# 7.4 Eligibility criteria for continued treatment in the extension period

Criteria for the transition to the extension period (V6/6a) and for continued treatment within the extension period (V10/10a and V14/14a) are listed below. (Note that the pairs of visits 6/6a, 10/10a and 14/14a will normally take place on the same respective day.)

If these eligibility criteria are not fulfilled at the end-of-cycle visit postponement of study treatment may take place at the beginning of the following injection cycle of the extension period. The re-injection visit can be postponed for up to a maximum of two weeks (but no longer than 18 weeks after the preceding treatment visit). For subjects who still do not fulfill the eligibility criteria at the revisit, study participation will be ended.

	Eligibility Criteria for Extension Treatment	Ratio- nale	Visits 6, 6a, 10, 10a, 14, 14a
1.	Clinical need for re-injection.	Ind	Х
2.	Absence of medically-relevant severe adverse events of special interest that are judged to have a causal relationship to the study treatment (indicative of toxin spread in the area of injection), especially respiratory arrest/distress/failure and dysphagia necessitating diet changes occurred during any period of the study.	Safety	Х
3.	No concomitant infection or inflammation in the head and neck region.	Safety	Х

Page 52 of 183

		Eligibility Criteria for Extension Treatment	Ratio- nale	Visits 6, 6a, 10, 10a, 14, 14a
4.	Neg fem	ative result of pregnancy test (testing only performed for ale with history of menarche, i.e. the first menstrual bleeding).	Safety	Х
5.	No :	significant risk of suicidality since last injection based on the Investigator's judgment, and	Safety	Х
	•	if appropriate, as indicated by a response of "no" to questions 4 or 5 in the suicidal ideation section of the C-SSRS		
	•	and no non suicidal self-injurious behavior		
	•	and no suicidal behavior.		

Definition of indication for continued study treatment [Ind]; administrative [Adm].

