## 9.2 Visit schedule

The purpose of the screening visit is to determine the subject's eligibility for study participation. The subject will be notified of any new diagnosis of an abnormal medical condition during the screening process, and will be referred for appropriate care. The screening evaluation must be completed 7–28 days (Table 6) before the baseline visit.

The baseline visit, at which the final decision on inclusion, the randomization (subjects aged 6-17 years only) of the subject and the administration of the first study treatment are performed, is defined as Day 1.

During the study, subjects will receive NT 201 (or, in the main period, matching placebo [subjects aged 6-17 years only]) at the beginning of each 16-week injection cycle. The visit schedules with study activities are shown in Table 6. For each study visit a time window is allowed, as detailed in Table 6 and described in Section 6.1.2.

The final study visit will take place after a total of  $64 \pm 8$  weeks, at the end of the fourth injection cycle. Since this will be as long as  $16 \pm 2$  weeks after the last administration of NT 201, no further visit for safety follow-up is planned.

At the physician's discretion, the final visit of each study injection cycle can be advanced by up to two weeks (e.g., if the physician considers earlier repeated treatment/assessment to be advisable) or postponed by up to two weeks (in the converse situation).

Unscheduled visits may be required in the case of premature discontinuation of study treatment. In this case, a final assessment (the end-of-study visit) will be performed. If additional safety follow-up is necessary after this assessment, subjects may be contacted by telephone or assessed in the clinic, depending on the nature of the follow-up required.

Table 6:Schedule of study tests, procedures and clinic visits

SOP/245/EN - CLINICAL STUDY PROTOCOL Version 2.0 Version 16-JUN-2016

Merz Pharmaceuticals GmbH

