#### Adverse Events

AEs will be coded according to the Medical Dictionary for Regulatory Activities (MedDRA) (version in effect when the database is closed).

TEAEs of MP are defined as AEs with onset or worsening after the first injection of NT 201 or Placebo up to and before first injection of the extension period or - in case of discontinuation before second injection – up to and including 16 weeks after first injection of NT 201 or Placebo or date of last study visit, whichever is later. AEs starting in the MP and not having resolved at the final visit of MP (V6) will be followed and further documented in the extension period.

TEAEs of OLEX are defined as AEs with onset or worsening after the first injection of OLEX up to and including 16 weeks after last injection or the date of last study visit, whichever is later.

A detailed description of the rules to be used for the classification of TEAEs can be found in Appendix 1. If an AE worsens between start and end of this AE it will be considered as new AE starting with the date of the worsening. In this case the imputation of end dates within episodes of the same AE will be done by setting the end date/end time to start date/start time of the consecutive worsening record.

In detail missing or partially missing start and stop dates of an AE will be imputed as follows for the calculation of the duration of an AE:

Page 26 of 46

- if start time is missing and date is given and not equal to first exposure date in MP or OLEX, set time to 00:00, else if date is equal to first exposure date in MP or OLEX set time to time of first exposure in MP or OLEX, if given (else 00:00), respectively
- if start time is missing and date is given and equal to the subsequent exposure date in OLEX (e.g. 2nd injection in OLEX), set time to time of the subsequent exposure, if given (else 00:00)
- if start date/time is completely missing and end date is not after or equal to first exposure of MP: no imputation.
- if start date/time is (partially) missing and end date is after or equal first exposure in MP or missing:
  - $\circ$  only start day is missing, but month and year same as first exposure in MP or OLEX: set day and time to day and time of first exposure, else set day to 1 and time to 00:00
  - Start day and month are missing, but year is the same as year of first exposure in the MP (which is ≠ year of first exposure in OLEX): set day, month, time to day, month, time of first exposure in the MP

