- If month, day and time are missing, but year is given and covering several OLEX cycles and the earliest possible OLEX cycle for assignment starts in the year before the AE start (but ends in the year of the AE start), month and day will be set to 1 and time to 00:00. If the earliest possible OLEX cycle for assignment starts in the year of the AE start, month/day/time will be set to month/day/time of the respective cycle start.

Calculation of time to duration of AEs [days]:

• The duration will be calculated as stop date - onset date + 1 for each episode of worsening of AE.

An overview summary table will be created for TEAEs and non-TEAEs displaying the frequencies and percentages of the following categories: "Any TEAE", "Any TEAE related to treatment", "Any TEAE of special interest", "Any TEAE of special interest related to treatment", "Any serious TEAE", "Any serious TEAE related to treatment", "Any TEAE leading to discontinuation", "Any TEAE leading to discontinuation related to treatment", "Any fatal TEAE" and "Any fatal TEAE related to treatment" for TEAEs and "Any non-TEAE", "Any non-TEAE", "Any serious non-TEAE", "Any non-TEAE", "Any serious non-TEAE", "Any non-TEAE leading to discontinuation" and "Any fatal non-TEAE" for non-TEAEs.

Incidences will be calculated for TEAEs, treatment-related TEAEs, serious TEAEs, related serious TEAEs, TEAEs leading to discontinuation, TEAEs of special interest at the system organ class level and at the preferred term level and will be presented by treatment, by injection cycle and overall (i.e. per period). TEAEs will also be presented by preferred term level, by treatment, injection cycle and overall. Additionally, TEAEs will be analyzed by worst intensity, by worst causal relationship and by worst outcome.

The number and percentage of subjects with at least one non-serious TEAE with incidence  $\geq =$  5% will be displayed by system organ class level and preferred term level.

In general, all safety analyses for OLEX will be performed overall and for the  $2^{nd}$ ,  $3^{rd}$  and  $4^{th}$  injection cycle. Only the number and percentage of subjects with at least one non-serious TEAE with incidence  $\geq = 5\%$  will be performed overall only.

Listings displaying incidences for TEAEs leading to discontinuation, serious TEAEs and TEAEs of special interest will also be provided.

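### NT 201 and placebo main-period TEAE percentages can cover somewhat different times at risk, because the window closes at a second injection timed partly by need; child-time rates should be shown beside them.

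*SAP*

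**What the plan says.** SAP 7.5 (Adverse Events) gives the main-period TEAE window two branches. For a child who goes on to the extension, it counts "AEs with onset or worsening after the first injection of NT 201 or Placebo up to and before first injection of the extension period". For a child who stops before the second injection, it runs "up to and including 16 weeks after first injection of NT 201 or Placebo or date of last study visit, whichever is later". The first branch has no fixed closing day.

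The date of the second injection is flexible. Protocol 9.2 says that, at the physician's discretion, "the final visit of each study injection cycle can be advanced by up to two weeks". The example it gives is "if the physician considers earlier repeated treatment/assessment to be advisable) or postponed by up to two weeks (in the converse situation". Protocol 7.4 makes "Clinical need for re-injection" the first of five conditions for extension treatment. If the conditions are not met, it adds: "The re-injection visit can be postponed for up to a maximum of two weeks (but no longer than 18 weeks after the preceding treatment visit". Protocol 6.2 sets a minimum separation of 14 weeks.

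For the summaries, SAP 7.5 plans an overview table "displaying the frequencies and percentages of the following categories", plus incidences by system organ class and preferred term. The SAP text mentions no event rate per unit of time, no common cut-off day and no time-to-first-event summary. SAP 7.6 (Duration of exposure) tabulates injection cycle length, including the classes below 14, 14–18 and above 18 weeks, but does not connect it to the AE tables.

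**The concern.** The comparison of NT 201 with placebo at ages 6–17 in the main period is the only controlled safety contrast in the trial, and TEAE occurrence is the primary safety variable. A crude percentage of children with at least one event rises with the length of time over which events are counted. Here that length is settled after randomization and depends in part on whether the child seems to need treatment again, which is what NT 201 is meant to change.

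If NT 201 holds off the return of drooling, placebo children may be re-injected somewhat earlier on average and NT 201 children somewhat later. NT 201 would then collect slightly more background events, such as infections, from extra time alone, and part of any excess could be read as a drug effect. A child who still shows no need at the postponed visit leaves the study and falls under the second branch, so that child's window can also run past week 16.

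**Working it through.** **Inputs from the documents.** Cycle length 16 ± 2 weeks (Protocol 6.1.2), minimum 14 weeks (6.2), maximum 18 weeks (7.4); 146 children on NT 201 and 73 on placebo (SAP 4).

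**Assumptions.** The documents give no AE risk and no re-injection timing by arm. I assume the same true hazard in both arms, with a 16-week risk p of at least one TEAE of 10%, 20% or 40%. The timing patterns below are also assumed.

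**1. The plan's own range.** Four cycles give 4 × 14 = 56 and 4 × 18 = 72 weeks, matching the stated 56–72. With 1 to 4 weeks of screening, 1 + 14 = 15 and 4 + 18 = 22 weeks, matching the stated main-period total of 15–22. For a child who continues, the window is therefore 14 to 18 weeks: a spread of 4 weeks, a ratio of 18/14 = 1.29.

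**2. Ceiling under a constant hazard.** h = −ln(1 − p)/16 and F(w) = 1 − exp(−h·w).

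| 16-week risk p | F(14) | F(18) | Gap, points |
|---|---|---|---|
| 10% | 8.8% | 11.2% | 2.4 |
| 20% | 17.7% | 22.2% | 4.5 |
| 40% | 36.0% | 43.7% | 7.7 |

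This needs every child in one arm at week 14 and every child in the other at week 18.

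**3. Modest timing difference.** Suppose 50% of placebo and 10% of NT 201 children are re-injected at week 14 and the rest at week 16. Mean windows are 0.5 × 14 + 0.5 × 16 = 15.0 and 0.1 × 14 + 0.9 × 16 = 15.8 weeks.

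- p = 40%: placebo 0.5 × 36.0 + 0.5 × 40.0 = 38.0%; NT 201 0.1 × 36.0 + 0.9 × 40.0 = 39.6%; gap 1.6 points.
- p = 20%: placebo 18.9%, NT 201 19.8%; gap 0.9 points.

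**4. Front-loaded events.** Let the hazard halve every 3 weeks: k = ln 2/3, c = −ln(1 − p)/(1 − exp(−16k)), F(w) = 1 − exp(−c(1 − exp(−k·w))). Even at 14 against 18 weeks, the results are 19.73% against 20.17% (p = 20%, gap about 0.4 points) and 39.54% against 40.29% (p = 40%, gap 0.75 points).

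**5. What a child-time rate does.** Under a constant hazard, the expected time to first event or window end is F(w)/h, so first events divided by child-time gives h whatever the window. At p = 40%, h = 0.0319 per child-week. The expected time is 0.360/0.0319 = 11.3 weeks for a 14-week window and 0.437/0.0319 = 13.7 weeks for an 18-week window. Both give 3.19 first events per 100 child-weeks, and the gap disappears.

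**6. Sampling error for scale.** The standard error of the difference is √[p(1 − p)(1/146 + 1/73)]: 7.0 points at 40% and 5.7 points at 20%.

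**The case against.** The case against is substantial.

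- The rule is the same in both arms, and physicians and carers are blinded (Protocol 8.5).
- Only one of the five conditions in Protocol 7.4 is clinical need. The others are severe related AESIs, head and neck infection or inflammation, pregnancy and suicidality. Protocol 9.2 mentions earlier re-treatment only as an example.
- Protocol 6.2 expects the effect to decay after 8–12 weeks, and Protocol 4.2 extended the interval to limit overlap of doses. On that premise, much of the difference in need has faded by week 14.
- Safety analysis is descriptive, and the cycle-length tables would show an imbalance.
- A plausible bias is well inside the sampling error.

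Much of this stands, and it limits the size. It does not remove the point. A blinded physician still acts on visible drooling, so a common rule can give different times at risk. Protocol 4.1.2 also reports a benefit of about three to four months in most children, in a passage on doses above 2.5 U/kg, so some difference at weeks 14–18 remains possible. A cycle-length table lets a reader see an imbalance but not correct for it. Sampling error does not cancel a systematic shift.

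A reader might go further and infer that the windows must differ between arms, or that an NT 201 excess of up to 7.7 points should be expected as an artefact. The documents support neither. They give no timing by arm, and 7.7 points needs the two extremes of timing together with a constant hazard and an assumed 40% risk.

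**Conclusion.** The point holds in a limited form. For children who continue, the window closes at an event that may fall from week 14 to week 18, partly according to perceived need, and the SAP text reports crude percentages without adjusting for time. Whether the arms will differ in timing is unknown. If NT 201 delays re-injection, its percentages are inflated relative to placebo.

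On the stated assumptions, the likely size is about 1 to 2 points for modest timing differences. It is under 1 point for early-onset effects, and 2.4 to 7.7 points is a ceiling for 10% to 40% risk. The issue therefore concerns late or background events, not acute injection effects. SAP Appendix 1, which holds the detailed TEAE rules and the table list, was not available and might already contain a rate table. This is a cheap improvement, not a flaw that invalidates the safety comparison.

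**What to change.** Leave the full-window main-period tables as they are. In SAP 7.5, add for NT 201 against placebo at ages 6–17, beside each percentage for TEAEs, TEAESIs and TESAEs, the number of children with a first event divided by total child-time at risk. Time at risk runs from the first injection to the first event of that type, the second injection or the end of the window, whichever comes first. Say also how time after a discontinuer's last contact is treated, because the 16-week branch can outlast actual observation.

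Do not replace the comparative table with a common cut-off at day 98 (14 × 7). After screening, main-period laboratory tests are taken only at V6 (Protocol 9.1.6, Table 5), and dental examinations only at Week 4 and V6 (Protocol 10.7). V6 is at week 16 ± 2. The cut-off would drop most findings first recorded there and keep them mainly for children seen early. A 14-week table is acceptable only as a supplement.

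The cost is one extra column or table; injection dates are already used for cycle length, and nothing changes in conduct or data collection. The downside is that child-time rates dilute early-onset events in the arm followed longer, so they must be read together with the percentages.

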  - Start day and month are missing, but year is the same as year of first exposure in the OLEX (which might be the same as year of first exposure in MP): set day, month, time to day, month, time of first exposure in OLEX
  - Start day and month are missing and year is not the same as year of first exposure in the MP or OLEX: else set day and month to 1 and time to 00:00
- if start date/time is completely missing and end date/time is at or after date/time of first exposure in the MP and before date/time of first exposure in OLEX, set start date/time to date/time of first exposure in the MP (e.g. AE start missing, AE end date 10CT2014, first injection MP: 1AUG2014).
- if start date/time is completely missing and end date/time is at or after date/time of first exposure in the OLEX, set start date/time to date/time of first exposure in the OLEX
- if AE end date and time are missing and date and time of study end (i.e. last contact or last visit of the study) are not missing, set end date/time to study end date/time, else set end date to study end date and time to 23:59.
- if AE end date/time is partially missing and given information on date is not equal to study end, set day to last day of the given month or day/month to 31/12 of the given year and missing time to 23:59.
- if AE end date/time is partially missing and year or year and month are equal to year or year and month of study end, set analysis end date/time to the date/time study end and missing time to 23:59.
- if AE end time is missing time will be set to 23:59
- if start date and end date is completely missing, set end date to study end date and time to 23:59. Estimate then missing start date as described above

In the following case a special rule will be applied:

If it is not clear in which OLEX cycle the AE starts, incomplete AE start dates/times will be replaced in such a way that the AE is assigned to the earliest possible cycle:

- if start time is missing but date is given and equal to any exposure date in OLEX and AE is assigned to the later cycle, time will be set to start of the later cycle. If AE is assigned to the previous cycle, time will be set to 0:00.
- If day and time are missing, but month and year are given and equal to any exposure date (month and year) in OLEX and AE is assigned to the later cycle, day and time will be set to start day and time of the later cycle. If AE is assigned to the previous cycle, day will be set to 1 and time to 00:00.

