Listings will be created for subjects who died, subjects with TEAEs of standard MedDRA query suicide/self-injury and for subjects with possibly suicidal events.

TEAEs for the  $2^{nd}$  injection cycle are defined as adverse events with onset or worsening at or after date of  $2^{nd}$  injection and before date of  $3^{rd}$  injection. TEAEs for the  $3^{rd}$  injection cycle are defined as adverse events with onset or worsening at or after date of  $3^{rd}$  injection and before date of  $4^{th}$  injection. TEAEs for the  $4^{th}$  injection cycle are defined as TEAEs with onset or worsening at or after 4th injection.

Duration of AEs will be listed only. Imputed values will be flagged as such.

In case of missing intensity or missing causal relationship of an AE the worst case principle will be applied, i.e. a missing intensity will be set to "severe" and a missing causal relationship will be set to "related". Missing data of the worst outcome will be imputed by "unknown". If a subject has more than one outcome within a preferred term (PT) only the worst outcome will be used in the frequency tables. Also on subject level only the worst outcome is defined in the following order:

- recovered/resolved
- recovered/resolved with sequelae
- recovering/resolving
- not recovered/not resolved
- unknown
- fatal.

For any missing data on seriousness a worst case strategy will be applied for all analysis tables. The AE will be regarded as 'serious'.

TEAESIs are defined as adverse events occurring after treatment that are thought to possibly indicate toxin spread. The list of adverse events of special interest possibly indicating toxin spread based on MedDRA version 22.0 (version in effect at database closure) is given in Table 4.

MedDRA Preferred Term (MedDRA version 22.0)		
Accommodation disorder	IIIrd nerve paresis	
Areflexia	Ileus paralytic	
Aspiration	IVth nerve paresis	
Botulism	Monoparesis	
Bradycardia	Muscular weakness	
Bulbar palsy	Paralysis	
Constipation	Paraparesis	
Cranial nerve palsies multiple	Paresis	
Cranial nerve paralysis	Paresis cranial nerve	
Diaphragmatic paralysis	Peripheral nerve palsy	
Diplopia	Peripheral paralysis	
Dry mouth: only when severe, serious, or outcome is not recovered, fatal or unknown	Pelvic floor muscle weakness	
Dysarthria	Pneumonia aspiration	
Dysphagia	Pupillary reflex impaired	
Dysphonia	Quadriparesis	
Dyspnoea	Respiratory arrest	
Extraocular muscle paresis	Respiratory depression	

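### SAP 7.5 imputes a year-only AE start to the first extension injection without testing the AE end date against that injection, so an AE that ended in the main period can be given a start after its end

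*SAP*

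**What the plan says.** All the rules are in SAP 7.5, Adverse Events, in the list on imputing missing AE dates. The list is introduced as serving the calculation of AE duration.

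- **Entry condition for partial starts:** "if start date/time is (partially) missing and end date is after or equal first exposure in MP or missing". The end date is compared with the first MP injection and with nothing else.
- **Year-only start:** where the "year is the same as year of first exposure in the OLEX (which might be the same as year of first exposure in MP", day, month and time are set to those of the first OLEX injection. The wording expressly foresees both injections falling in one calendar year.
- **Day-only gap:** where "only start day is missing, but month and year same as first exposure in MP or OLEX", day and time are set to those of that first exposure.
- **Completely missing start:** "if start date/time is completely missing and end date/time is at or after date/time of first exposure in the MP and before" the first OLEX injection, the start is set to the first MP injection. The worked example cites "first injection MP: 1AUG2014" and an AE end of 1 October 2014.
- **Special rule for doubt about the OLEX cycle:** "incomplete AE start dates/times will be replaced in such a way that the AE is assigned to the earliest possible cycle".

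The same section ends the MP window for TEAEs "up to and before first injection of the extension period". TEAEs for the second "injection cycle are defined as adverse events with onset or worsening at or after date of" the second injection. The detailed TEAE classification rules are referred to Appendix 1. Duration is stop minus onset plus 1. It is only listed, and imputed values are flagged.

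**The concern.** An imputation rule should not contradict a date that is actually recorded. Here it can. The year-only rule chooses the later of two candidate injections and never asks whether the AE was already over by then. A record with no start information at all is handled correctly, while a record whose start year is known can receive an impossible start.

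The certain consequence is a duration of zero or less in the AE listing. The possible consequence is larger. Occurrence of TEAEs, shown per period and by cycle, is the primary safety variable, and the MP is the only part of the study with a placebo group. If the imputed start is also used to place the AE, an event from the MP would be counted in OLEX cycle 2. For a subject randomised to placebo, an event under placebo would then appear under NT 201.

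**Working it through.** **1. The SAP's own example, start completely missing.** First MP injection 1 August 2014, AE end 1 October 2014. The rule sets the start to 1 August. Duration = 61 + 1 = 62 days.

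**2. The same AE with the start recorded as 2014.** The example gives no OLEX date, so I take the allowed 14, 16 and 18 weeks after the MP injection. All three dates fall in 2014, so the year-only rule applies.

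| Interval | First OLEX injection = imputed start | Duration (stop - onset + 1) |
|---|---|---|
| 14 weeks | 7 November | -37 + 1 = -36 days |
| 16 weeks | 21 November | -51 + 1 = -50 days |
| 18 weeks | 5 December | -65 + 1 = -64 days |

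The entry condition does not stop this, because 1 October is after the first MP injection.

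**3. A second illustration.** MP injection 1 February, OLEX injection 24 May (112 days later in a non-leap year), start year known, AE end 10 March. The imputed start is 24 May and the duration is -75 + 1 = -74 days. In general, a known end k days before the first OLEX injection gives a duration of 1 - k, which is zero or negative for every k of 1 or more.

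**4. Injections in different years.** MP injection 3 October 2016, OLEX injection 23 January 2017, start recorded as 2017, AE end 15 January 2017. The imputed start is 23 January and the duration is -8 + 1 = -7 days. The fault is therefore not limited to same-year injections.

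**5. Day-only gap.** With the injections in step 3, suppose the start is recorded as May and the end as 10 May. The imputed start is 24 May and the duration is -14 + 1 = -13 days. This holds unless the special rule applies. One of its bullets covers a missing day in the month of any OLEX exposure and sets the start to day 1 if the AE belongs to the previous cycle. Its lead-in, however, limits it to doubt between OLEX cycles.

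**6. How often the condition could be met.** This assumes MP injection dates uniform over a 365-day year. Both injections share a calendar year for (365 - 112)/365 = 69% of subjects at 16 weeks, (365 - 98)/365 = 73% at 14 weeks and (365 - 126)/365 = 65% at 18 weeks. With onset also uniform over a 16-week MP, a year boundary lies between onset and the OLEX injection with average probability 56.5/365 = 15%. About 85% of year-only AEs with onset in the MP would therefore be dated to the OLEX injection. For AEs lasting 1, 7, 14 or 28 days, enumeration under the same assumptions gives a start after the end in 85%, 79%, 73% and 61%. These shares are conditional on a year-only record in a subject who went on to an OLEX injection. They say nothing about how many such records exist.

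**The case against.** The strongest reply is that the list is stated to serve AE duration, that duration is only listed with imputed values flagged, and that TEAE classification is governed by Appendix 1. The special rule supports this reading in part. Its lead-in ties replaced dates to cycle assignment, but its bullets on missing times and days take the assignment as given and set the date to match. That fits classification being done elsewhere, and the rule concerns OLEX cycles, not MP versus OLEX. This objection stands as far as it goes. A reader might infer that the rule does move MP events into open-label data, but the documents do not establish it. They also do not exclude it, because the SAP text gives no other rule for placing a year-only AE in the MP or OLEX.

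Three further points on the other side:

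- It would be wrong to say that there is no end-date check. There is one, against the first MP injection. The missing check is against the first OLEX injection.
- Affected records should be few. Protocol 10.1 requires the onset date and collects AEs at each visit, MP visits are about four weeks apart, and Protocol 11.3 and 11.4 provide for queries and monitoring.
- Where the end date does not settle the period, choosing the later period has a rationale. In placebo subjects it attributes ambiguous events to active drug, in line with the SAP's worst-case handling of missing causality and seriousness. Choosing the earliest period is not clearly better.

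None of this removes the impossible start when the end date is known.

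**Conclusion.** The rule is wrong as written. For a subject with an OLEX injection, an AE whose start year is that of the first OLEX injection, and whose documented end lies between the first MP and first OLEX injections, always receives a start after its end. The size is -36 to -64 days on the SAP's own example dates and -74 days in the second illustration. The day-only rule shares the gap unless the special rule's bullet is meant to cover it.

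The practical effect is probably small. The number of year-only records is not given. The 69% is the share of subjects with both injections in one calendar year under assumed uniform enrolment, and should not be read as a rate of affected AEs. Loss of events from the placebo-controlled comparison is possible only if the imputed dates feed TEAE classification, which depends on Appendix 1. Otherwise the fault stays within flagged listing values. Efficacy analyses are not touched.

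**What to change.** Add to both partial-date rules (year only, and missing day) the end-date test that SAP 7.5 already uses for completely missing starts:

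- If the known end is before the first OLEX injection, set the start to the later of the first MP injection and the first day of the known year or month.
- Never impute a start after a known end.
- State whether the special rule's bullet on a missing day covers the first OLEX injection.
- Confirm that the result agrees with the TEAE classification in Appendix 1.

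With this change the examples give:

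- SAP dates: start 1 August 2014, duration 62 days.
- 1 February case: start 1 February, duration 37 + 1 = 38 days.
- Cross-year case: start 1 January 2017, duration 14 + 1 = 15 days.
- Day-only case: start 1 May, duration 9 + 1 = 10 days.

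The tie-break for AEs whose end date does not settle the period is for the sponsor to choose and state. The cost is one or two lines of SAP text and derivation code before unblinding, with no new data.
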